16.2 ClinicalTrials.gov Study Registration

This clinical study, ATB-203, will be registered on www.ClinicalTrials.gov prior to enrollment of the first patient. Patients are to be made aware of this study registration through the informed consent process prior to study participation. Final study results will be posted on ClinicalTrial.gov according to US regulatory guidelines.

16.3 Publication Policy

By signing the study protocol, the Investigator agrees with the use of results of the study for the purposes of national and international registration, publication and information for medical and pharmaceutical professionals. If necessary, Regulatory Authorities will be notified of the Investigator's name, address, qualifications, and extent of involvement.

An Investigator shall not publish any data (poster, abstract, paper, etc.) without having consulted with the Sponsor in advance. Details are provided in a separate document.

18. APPENDICES

18.1 Appendix A - Study Visits and Procedures

Visit	1 Screening ^a	2 Day 1	3 Day 2	4 Day 3	5 Day 7 ±1 day	6 Day 10 ±1 day	7 Day 14 ±1 days	8 Day 21 ±1 days	9 Day 29 +3 days	10 3 to 21 Days after Visit 9	11 Day 90 +5 days
Informed Consent	X										
Demographics	X										
Medical History	X										
Lesion History (NSTI)	X										
Concomitant Medications ^b											
Weight & Height ^c	X				X		X		X		
Fluid Balance (input/output)											
Detailed Urine Output ^d											
Vital Signs ^e	X	X	X	X	X	X	X	X	X		
Physical Examination (PE)	X				X		X				
Interim PE (symptom-driven)		X		X		X					

^a Screening period can be 48 hours after suspected diagnosis of abdominal infection

^b See Section 9.2.5 for instruction on level of detailed information required for recording concomitant medications

^c Height will be taken only at screening or first time that patient height can be measured

^d Urine output is required for Days 1-7 (while the patient is in the ICU or step-down unit (or equivalent); patients on a general ward only monitor urine output if a Foley catheter is in place as part of standard of care) to assess for development or resolution of acute kidney injury

^e Systolic & diastolic blood pressure, mean arterial pressure, heart rate, respiration rate, temperature; (first set of vitals on that visit day)

Visit	1 Screening ^a	2 Day 1	3 Day 2	4 Day 3	5 Day 7 ±1 day	6 Day 10 ±1 day	7 Day 14 ±1 days	8 Day 21 ±1 days	9 Day 29 +3 days	10 3 to 21 Days after Visit 9	11 Day 90 +5 days
Baseline Signs & Symptoms ^f	X										
Blood Chemistry ^g	X ^h	X ⁱ	X ^j	X ⁱ	X	X ^j	X	X ^j	X ^k	X ⁱ	X ^j
Spot Urine Albumin/ Creatinine ^l	X	X		X	X		X		X		X
Standard C- Reactive Protein ^m	X				X		X		X		
Blood Hematology ⁿ	X	X		X	X		X		X		
Pregnancy Test (if applicable) ^o	X										
Serum for Immunogenicity ^p	X						X		X		X
Urine and Plasma for Storage ^q	X		X		X						

^f Adverse events reported from ICF signature to Reltecimod administration

^g Glucose; Electrolytes - Sodium, Potassium, Calcium; Phosphorus, Chloride, Bicarbonate; Renal function tests – Urea/BUN, Creatinine; Liver function tests – Albumin, Bilirubin Total, Alanine transaminase (ALT), Aspartate transaminase (AST), Alkaline phosphatase (ALP), Protein Total. In case of abnormal results at the end of the study the results should be followed by the investigator until the abnormalities are resolved or determined as stabilized

^h If AKI diagnosis not established at time of initial evaluation for abdominal infection, then obtain creatinine every 6 hours for up to 48 hours after suspected or confirmed diagnosis of abdominal infection to identify development of AKI

ⁱ Only creatinine and bilirubin

^j Only creatinine

^k Creatinine and albumin only

^l Obtain urine specimen for spot albumin/creatinine ratio. First morning void is preferred

^m Use standard CRP test (do not use cardiac or high-sensitivity CRP)

ⁿ Complete blood count including platelet count and white blood cell differential

^o Preferably the fastest pregnancy test method (urine or blood)

^p 6 mL blood for serum for storage (for immunogenicity testing) at screening, Days 14, 29, and 90

^q Obtain 5 mL urine and 5 mL blood for plasma for storage for AKI biomarker analysis. Second sample to be collected 24±6 hours (Day 2) after study medication administration. Final sample to be obtained at Day 7

Visit	1 Screening ^a	2 Day 1	3 Day 2	4 Day 3	5 Day 7 ±1 day	6 Day 10 ±1 day	7 Day 14 ±1 days	8 Day 21 ±1 days	9 Day 29 +3 days	10 3 to 21 Days after Visit 9	11 Day 90 +5 days
Systemic Inflammatory Biomarkers • RNA ^r • Cytokines / Chemokines ^s	X X	X X	X X	X X							
Arterial Blood Gases (if applicable)	X	X		X	X		X				
SpO2 and FiO2 (if arterial blood gases not indicated or unable to obtain)	X	X		X	X		X				
Peritoneal Fluid, Tissue or Abscess Fluid for Abdominal Infection, or Tissue for NSTI for Microbiology	X										
Inclusion & Exclusion ^t	X										
Randomization	X										

^r 5 mL (2 x 2.5 mL) of whole blood to be collected at screening, Day 1 at 4 to 6 hours post-dose, Day 2 at 24 ±4 hours post dose, Day 3 at 48 hours ±4 hours post-dose, and Day 4 72 ±4 hours post dose. Complete blood count with white blood cell differential to be obtained at same time of whole blood for genomic profile sample

^s Systemic Biomarkers will be taken at screening, 4 to 6 hours, 24±4, 48±4 and 72±4 hours post drug administration; However, if practical consideration allow collection of fewer plasma samples, this will not be considered a protocol deviation. Systemic blood inflammatory biomarkers will include serum cytokines or chemokines such as (but not limited to): IL-6, IL-8, INF-γ, TNF-α, IL-17A, IL-3 and RANTES.

^t Should be verified twice: a full list of criteria will be verified once before instructing the pharmacist to prepare study drug and a second time immediately before study drug administration according to a partial list to include verification that 6 hours has not elapsed from time to study drug administration

Visit	1 Screening ^a	2 Day 1	3 Day 2	4 Day 3	5 Day 7 ±1 day	6 Day 10 ±1 day	7 Day 14 ±1 days	8 Day 21 ±1 days	9 Day 29 +3 days	10 3 to 21 Days after Visit 9	11 Day 90 +5 days
Reltecimod / Placebo Administration		X									
Blood Culture ^u	X										
Adverse Events / Serious Adverse Events ^v	w 										
Lesion Assessment (NSTI) ^x	X	X	X	X	X	X	X				
Collect data on Additional Amputations (NSTI)											
Collect Data on Acute Renal Replacement Therapy											
Collect Data on Renal Imaging											
Collect Data on Additional Renal Procedures (e.g., Renal Biopsy)											
Record any Follow-up Surgical or											

^u Blood culture for both aerobic and anaerobic bacteria will be repeated during the study in case of new systemic infection suspicion

^v Adverse events including SAEs will be collected from obtaining ICF through day 28; AEs that are not resolved should be followed-up until resolution or until determined as stable and due to known cause

^w AEs of Screening are baseline AEs (not TEAE) starting after obtaining ICF until study drug administration

^x Assess lesion status (healing/progression/significant change in appearance) if accessible for visible assessment at time of debridement or routine dressing change

Visit	1 Screening ^a	2 Day 1	3 Day 2	4 Day 3	5 Day 7 ±1 day	6 Day 10 ±1 day	7 Day 14 ±1 days	8 Day 21 ±1 days	9 Day 29 +3 days	10 3 to 21 Days after Visit 9	11 Day 90 +5 days
Interventional Radiologic Procedures for Previously Documented Abdominal Infection											
Evaluation of Adequacy of Antimicrobial Treatment				X							
Critical Care and Hospital Stay Parameters ^y											
SOFA Score ^z	X	X ^{aa}		X	X		X				
APACHE II Score ^{bb}	X										
Survival											
Hospital Readmissions									X		X ^{cc}

^y Hospital length of stay (days), ICU stay (days), ICU free days, mechanical ventilation days/mechanical ventilation free days

^z Screening SOFA: To include measurements of 6 organ system: cardiovascular, respiratory, renal coagulation, GI/hepatic and CNS (To include evaluation of oxygenation either directly by arterial blood gas test or by calculation of PaO₂ from SpO₂, in case it is not possible to obtain arterial blood to determine the SOFA respiratory parameter)

^{aa} Subsequent SOFA measurement (Days 1, 3, 7, and 14): taken once a day, in the morning adjusted to the time of normal routine assessment activities. To be calculated retrospectively. The following blood samples must be taken: CBC with platelet count, serum creatinine and bilirubin. In addition, clinical parameters should be evaluated and recorded (see Section 18.3)

^{bb} For the required laboratory and clinical parameters (see Section 18.2 of the protocol)

^{cc} Capture data on any readmissions within 30 days of original hospital discharge

18.2 Appendix B – APACHE II Score

APACHE II Score:

- For each variable used in the APACHE II Score, the value from the previous 24 hours yielding the most points should be used
- Since it is not possible to assess the Glasgow Coma Scale (GCS) in patients who are sedated and paralyzed, by convention it is regarded as normal, unless it is known that there was a brain injury prior to sedation, as in the case of head injury (but not confusion associated with tiredness, hypoxia, etc.). This will result in a GCS of 15 and a neurologic score of 0 (zero).
- Chronic Health Evaluation

If any of these conditions are marked "Y", assign points based on the patient's condition at the time of ICU admission (or in the 24-hour period prior to screening) - See Section C on last page.

Organ insufficiency or immuno-compromised state must have been evident prior to this hospital admission and conform to the following criteria.

LIVER: Biopsy-proven cirrhosis and documented portal hypertension. or episodes of past upper GI bleeding attributed to portal hypertension, or prior episodes of hepatic failure/encephalopathy/coma. Y N

CARDIOVASCULAR: New York Heart Association Class IV. Y N

RESPIRATORY: Chronic restrictive, obstructive, or vascular disease resulting in severe exercise restriction, (i.e., unable to climb stairs or perform household duties); or documented chronic hypoxia, hypercapnia, secondary polycythemia, severe pulmonary hypertension (>40 mm Hg), or respirator dependency. Y N

RENAL: Receiving chronic hemo- or peritoneal dialysis. Y N

IMMUNO-COMPROMISED:

(1) The patient has received therapy that suppresses resistance to infection, eg immuno-suppressive agents, chemotherapy, radiation, long term low dose steroids, 10 mg/day prednisone for >1 month prior to hospitalization) or recent high dose steroids (> 15 mg/kg/day of hydrocortisone or >3 mg/kg/day of methylprednisolone for >5 days). Y N

(2) The patient has a disease that is sufficiently advanced to suppress resistance to infection, eg leukemia, lymphoma, AIDS, documented diffuse metastatic cancer. Y N

Physiologic Variable		HIGH ABNORMAL RANGE (Check one range per variable and write the severity score in the column to the right. Note: use the worst possible score for all variables, except for the GCS score.)					LOW ABNORMAL RANGE				Severity Score
Severity Points		+4	+3	+2	+1	0	+1	+2	+3	+4	
1	Temperature – rectal (°C)	 ≥41°	 39-40.9°		 38.5°-38.9°	 36°-38.4°	 34°-35.9°	 32°-33.9°	 30°-31.9°	 ≤29.9°	
2	Mean Arterial Pressume (mmHg)	 ≥160	 130-159	 110-129		 70-109		 50-69		 ≤49	
3	Heart Rate (Ventricular Response)	 ≥180	 140-179	 110-139		 70-109		 55-69	 40-54	 ≤39	
4	Resp. Rate (non-ventilated or ventilated)	 ≥50	 35-49		 25-34	 12-24	 10-11	 6-9		 ≤5	
5	Oxygenation: a. FIO ₂ ≥ 0.5 record A·aDO ₂ *	 ≥500	 350-499	 200-349		 <200					
	b. FIO ₂ < 0.5 record only PaO ₂					 PaO ₂ >70	 PaO ₂ 61-70		 PaO ₂ 55-60	 PaO ₂ <55	
6	Arterial pH	 ≥7.7	 7.6-7.69		 7.5-7.59	 7.33-7.49		 7.25-7.32	 7.15-7.24	 <7.15	
7	Serum Sodium (mmol/L)	 ≥180	 160-179	 155-159	 150-154	 130-149		 120-129	 111-119	 ≤110	
8	Serum Potassium (mmol/L)	 ≥7	 6-6.9		 5.5-5.9	 3.5-5.4	 3-3.4	 2.5-2.9		 <2.5	
9	Serum Creatinine (µmol/L) (double point score for acute renal failure)	 ≥309.4	 176.8-309.3	 132-177		 53-133		 <53			
10	Hematocrit (%)	 ≥60		 50-59.9	 46-49.9	 30-45.9		 20-29.9		 <20	
11	White Blood Count (total/mm ³) (in 1000s)	 ≥40		 20-39.9	 15-19.9	 3-14.9		 1-2.9		 <1	
12	Glasgow Coma Score (GCS) Score=15 minus actual GCS	(Note: The best GCS used for the 1 st 24 hours)									(15 - GCS Total)
		Eye	Verbal	Motor	GCS Total (= Eye + Verbal + Motor)						
A=Total ACUTE PHYSIOLOGY SCORE (APS): Total severity points indicated for Variables 1-12 in the column to the right.											
	Serum HCO ₃ (venous-mmol/L) (Use in place of variable 5 if no ABGs)	 ≥52	 41-51.9		 32-40.9	 22-31.9		 18-21.9	 15-17.9	 <15	

* A·aDO₂ = [(FIO₂ (713)-(PaCO₂/0.8)]-PaO₂

18.3 Appendix C – SOFA Score

Value	0	1	2	3	4
Respiratory PaO₂/FiO₂¹	>400	≤400	≤300	≤200 with respiratory support	≤100 with respiratory support
Coagulation Platelets	>150	≤150	≤100	≤50	≤20
GI Total Bilirubin³	<1.2	1.2-1.9	2.0-5.9	6.0-11.9	≥12.0
Cardiovascular²	No hypo- tension	MAP <70	Dopa ≤5 PE <100	Dopa > 5 Epi ≤ 0.1 NE ≤ 0.1 PE 100- 300	Dopa>15 Epi>0.1 NE>0.1 PE>300 VP>0.01
Neuro GCS	15	13-14	10-12	6-9	<6
Serum Creatinine³ OR Urine Output	<1.2	1.2-1.9	2.0-3.4	3.5-4.9 <500cc/ day	≥5.0 <200cc/ day

1. For patients on supplemental oxygen via nasal cannula, nasopharyngeal catheter or mask and for converting SpO₂ values to PaO₂ use the attached oxygen conversion tables.

2. Doses of dopamine (Dopa), epinephrine (Epi), norepinephrine (NE) are in micrograms/kg/min; phenylephrine (PE) is micrograms/min; vasopressin (VP) is U/min. Vasopressors must have been administered for at least one hour.

3. Total bilirubin and creatinine are in mg/dL.

Oxygen Conversion Tables

SpO ₂ (%)	PaO ₂ (mmHg)
80	44
81	45
82	46
83	47
84	49
85	50
86	52
87	53
88	55
89	57
90	60
91	62
92	65
93	69
94	73
95	79
96	86
97	96
98	112
99	145

Estimating FiO₂

Method	O ₂ flow	Estimated FiO ₂ (%)
Nasal cannula	1	24
	2	27
	3	30
	4	33
	5	36
	6	40
Nasopharyngeal catheter	4	40
	5	50
	6	60
Face mask	5	40
	6-7	50
	7-8	60
Face mask with reservoir	6	60
	7	70
	≥8	80

18.4 Appendix D – Glasgow Coma Scale

Enter one score for each response (Eyes, Motor and Verbal).			
Eyes Open	Motor Responses	Verbal – Non-Intubated	Verbal – Intubated
4 = spontaneously 3 = to verbal 2 = to painful stimuli 1 = no response	6 = to verbal command 5 = localized to pain 4 = withdraws to pain 3 = decorticate 2 = decerebrate 1 = no response	5 = oriented and converses 4 = disoriented and talks 3 = inappropriate words 2 = incomprehensible words 1 = no response	5 = seems able to talk 3 = questionable ability to talk 1 = generally unresponsive
Total Glasgow Coma Score (Eyes + Motor + Verbal)			

18.5 Appendix E – AKI Staging (KDIGO Criteria)

Stage	Serum Creatinine	Urine Output ¹
1	1.5-1.9 times baseline OR ≥0.3 mg/dL increase	< 0.5 mL/kg/h for 6 h
2	2-2.9 times baseline	< 0.5 mL/kg/h for 12 h
3	3 times baseline OR Increase in serum creatinine to ≥4 mg/dL OR Initiation of renal replacement therapy	< 0.3 mL/kg/h for 24 h OR Anuria for ≥12 h

1. Urine output should be calculated using IBW (using the Miller Formula). Urine output for patients in a non-ICU setting (e.g., general ward) can only be used to assess AKI staging if urine collection (and subsequent recording) is obtained from patients with a Foley catheter in place as part of standard of care.

18.6 Appendix F – Twice the Serum Creatinine for Age, Race, and Gender

Age (years)	Black Males mg/dL (μmol/L)	Other Males mg/dL (μmol/L)	Black Females mg/dL (μmol/L)	Other Females mg/dL (μmol/L)
20 – 24	3.0 (266)	2.6 (230)	2.4 (212)	2.0 (166)
25 – 29	3.0 (266)	2.4 (212)	2.2 (194)	2.0 (166)
30 – 39	2.8 (248)	2.4 (212)	2.2 (194)	1.8 (160)
40 – 54	2.6 (230)	2.2 (194)	2.0 (176)	1.8 (160)
55 – 65	2.6 (230)	2.2 (194)	2.0 (176)	1.6 (142)
>65	2.4 (212)	2.0 (166)	1.8 (160)	1.6 (142)

18.7 Appendix G - Immunosuppressive Agents

Immunosuppressive Agent^a	Upper Limit Dosage Use
1. Corticosteroid	> 40 mg/day of prednisone or its equivalent daily for > 2 weeks
Equivalent Dose (mg)	
a) Prednisone	40 mg
b) Hydrocortisone	160 mg
c) Methylprednisolone	32 mg
d) Dexamethasone	6 mg
e) Cortisone	200 mg
f) Betamethasone	4.8 mg
2. Methotrexate (Rheumatrex, Trexall)	Excluded at any dose
3. Leflunomide (Arava)/Teriflunomide (Aubagio)	Acceptable if being used as monotherapy
4. Cyclophosphamide (Cytosan)	Excluded at any dose
5. Cyclosporine A	Excluded at any dose (ophthalmic formulation (Restasis) is permitted)
6. FK506 (Tacrolimus)	Excluded at any dose (optical formulation (Protopic) is permitted)
7. Azathioprine	Excluded at any dose
8. Cancer Chemotherapy	Patients receiving cancer chemotherapy in the previous 4 weeks are excluded
9. Mycophenolate Mofetil (MMF) (CellCept)	Excluded at any dose (all solid organ and bone marrow transplant patients are excluded)
10. Sirolimus (Rapamycin, Rapamune)	Excluded at any dose
11. Everolimus (Certican)	Excluded at any dose
12. Temsirolimus (Torisel)	Excluded at any dose
13. Gusperimus	Excluded at any dose

14. Thalidomide	Patients receiving Thalidomide within the last 72 hours are excluded.
Immunosuppressive Agent^a	Upper Limit Dosage Use
Biologics	
(a) Anti-tumor necrosis factor (TNF) agents - Entanercept (Enbrel) - Entanercept (Enbrel) - Afelimomab (Fab 2) - Infliximab (Remicade) - Certolizumab (Cimzia) - Golimumab (Simponi)	Patients receiving Anti-TNF drugs within the last 8 weeks are excluded.
(b) Interleukin-1 Receptor Antagonist (IL-1RA) - Kineret	Patients receiving IL-1RA within the last 8 weeks are excluded.
(c) CTLA-4 Fusion Protein - Abatacept (Orencia) - Alefacept (Amevive) - Belatacept (Nulojix)	Patients receiving CTLA-4 Fusion protein within the last 8 weeks are excluded.
(d) Anti-CD20 - Rituximab (Rituxan/MabThera) - Obintuzumab (Gazyva) - Ocrelizumab (Ocrevus) - Ofatumumab (Arzerra)	Patients receiving Anti-CD20 drugs within the last 2 years are excluded.
(e) Anti-CD52 - Alemtuzumab (Campath)	Patients receiving Anti-CD52 drugs within the last 2 years are excluded.
(f) Anti-IL2 - Daclizumab (Anti-Tac, Zenapax) - Basiliximab (Simulect)	Patients receiving Anti-IL2 drugs within the last 2 years are excluded.

(g) Anti-IL6 - Tocilizumab (Actemra/RoActemra)	Patients receiving Anti-IL-6 drugs in the last 2 years are excluded.
(h) Anti-IL12/13 - Ustekinumab (Stelara)	Patients receiving Anti-IL 12/13 drugs in the last 2 years are excluded.
(i) Anti-BAFF (B-cell activating factor) - Belimumab	Patients receiving Anti-BAFF drugs in the last 8 weeks are excluded.
(j) Integrin Inhibitor - Natalizumab (Tysarbi)	Patients receiving Integrin Inhibitor drugs in the last 2 years are excluded.
(k) Anti-CTLA 4 - Ipilimumab	Patients receiving Anti-CTLA 4 drugs in the last 8 weeks are excluded.
(l) Other Interleukins - Aldesleukin (Proleukin) - Canakinumab (Ilaris) - Oprelvekin (Neumega)	Patients receiving any of these Interleukin drugs in the last 2 years are excluded.
(m) Anti-PDL1 - Avelumab (Bavencio)	Patients receiving any Anti-PDL1 drugs in the last 2 years are excluded.
(n) Other Selective Immunosuppressants - Muromonab or OKT-3: - Efalizumab (Raptiva): anti-CD11a - Fingolimod (Gilenya): Sphingosine 1-phosphate receptor modulator - Eculizumab (Soliris): anti-complement protein C5 - Tofacitinib (Xeljanz): JAK-STAT Inhibitor	Patients receiving any of these drugs in the last 3 months are excluded.

- Apremilast (Otezla): PDE-4 inhibitor- Vedolizumab (Entyvio): Integrin $\alpha_4\beta_7$	Patients receiving any of these drugs in the last 2 years are excluded.
---	---

^a For agents not listed, patients should be off such therapies for a time sufficient to restore immune function.

10	Deviations from the Original Statistical Plan.....	42
11	Appendix 1: Tables and Listing TOC.....	43
12	Appendix 2: AE Listings.....	52
13	Appendix 3: Patient Listings.....	53
14	Appendix 5: Study Visits and Procedures.....	55
15	Appendix 6: Clinical Score Calculations.....	60
15.1	AKI Staging (KDIGO Criteria).....	60
15.2	Twice the Serum Creatinine for Age, Race, and Gender.....	61
15.3	SOFA – Sequential Organ Failure Assessment Score.....	62
16	Appendix 7: Prior and Concomitant Medications.....	63
16.1	Nephrotoxic Medications.....	63
16.2	Immunosuppressant Medications.....	63
17	Appendix 8: CKD Definition and Classification.....	66
17.1	CKD Definition:.....	66
17.2	CKD Classification.....	66

1 Purpose and Scope of SAP

The purpose of this Statistical Analysis Plan (SAP) is to provide details regarding the analyses sets, endpoints, and statistical analysis methods to be used to meet the objectives of this trial. When differences exist in descriptions or explanations in the Clinical Study Protocol and this SAP, the SAP prevails. This SAP will be finalized prior to unblinding of the treatment allocation codes.

This document is designed to be a stand-alone document in terms of conveying essential statistical approaches to the analysis of the data. Additional definitions and details regarding variables collected are provided in the Clinical Study Protocol.

Statistical approaches were developed to be consistent with accepted statistical and clinical trial principles including ICH E9, Statistical Principles for Clinical Trials¹.

¹ ICH E9 Expert Working Group. Statistical Principles for Clinical Trials: ICH Harmonized Tripartite Guideline. *Statistics in Medicine* 1999; 18:1905–1942.

2 Key Elements of the Analysis Plan

2.1 Primary Efficacy Analysis

2.1.1 Primary Superiority Hypothesis

The primary effectiveness endpoint is *freedom from durable loss of renal function at Day 28*. Success requires:

- Alive at Day 28,
- Free of dialysis at Day 28, and
- Less than a 37% loss of estimated Glomerular Filtration Rate (eGFR; measured with the Modification of Diet in Renal Disease (MDRD) formula from the patient's reference eGFR) at Day 28.

Reference creatinine values, baseline AKI stage and percentage loss of eGFR will be determined through algorithmic determination (see details below). Percentage loss of eGFR determined algorithmically will be based on a comparison of eGFR at screening compared to an algorithmically determined reference creatinine value.

The primary efficacy comparison involves testing the following one-sided superiority hypotheses: **H₀: $\pi_{0.50} - \pi_{\text{placebo}} \leq 0$ vs H_a: $\pi_{0.50} - \pi_{\text{placebo}} > 0$** ; where $\pi_{0.50}$ and π_{placebo} represent the true probability of freedom from durable loss of renal function at Day 28. Each probability represents the proportion of subjects on each arm expected to achieve complete recovery. These hypotheses will be tested using a one-sided type 1 error rate of $\alpha=0.05$. The null hypothesis will only be rejected if the investigational drug demonstrates superiority. An unadjusted chi-square test will be used to test this hypothesis.

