10.1 Primary Efficacy Measure

- Rates of achieving the primary endpoint of freedom from durable loss of renal function (defined as alive, free of dialysis, and less than a 37% loss of eGFR (measured with the MDRD formula from the patient’s reference eGFR)) at Day 28.

AKI stage and recovery will be determined by a blinded adjudication committee as described in Section 10.4.

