12. STATISTICS

12.1 Primary Effectiveness Endpoint

The primary effectiveness endpoint for this study is:

- Rates of achieving the primary endpoint of freedom from durable loss of renal function (defined as alive, free of dialysis, and less than a 37% loss of eGFR; (measured with the MDRD formula from the patient's reference eGFR)) at Day 28.

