3.10.3 Day 28 eGFR

Day 28 eGFR will be determined by converting Day 28 creatinine to Day 28 eGFR using the following formula:

$$\text{Day 28 eGFR (mL/min/1.73 m}^2\text{)} = 175 \times (\text{Cr Day 28})^{-1.154} \times (\text{Age})^{-0.203} \times (0.742 \text{ if female}) \times (1.212 \text{ if African American}).$$

Percentage loss in eGFR at Day 28 will be determined using the following formula.

$$\text{Percentage loss in eGFR at Day 28} = 100\% \text{ times } [\text{Screening eGFR} - (\text{Day 28 eGFR}) / \text{Screening eGFR}]. \text{ If percentage loss } \geq 37\% \text{ then patient fails key secondary endpoint.}$$

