3.10.4 Day 14 eGFR

Day 14 eGFR will be determined by converting Day 14 creatinine to Day 14 eGFR using the following formula:

$$\text{Day 14 eGFR (mL/min/1.73 m}^2\text{)} = 175 \times (\text{Cr Day 14})^{-1.154} \times (\text{Age})^{-0.203} \times (0.742 \text{ if female}) \times (1.212 \text{ if African American}).$$

Percentage loss in eGFR at Day 14 will be determined using the following formula.

Percentage loss in eGFR at Day 14 = 100% times [Screening eGFR - (Day 14 eGFR) / Screening eGFR]. If percentage loss $\geq 37\%$ then patient fails the Day 14 endpoint.

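### The SAP's only formulas for eGFR loss start from the screening value, taken during AKI, and not from the reference eGFR that defines the primary endpoint

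*SAP*

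**What the plan says.** **Definition.** Protocol 12.1 sets the eGFR component as "less than a 37% loss of eGFR; (measured with the MDRD formula from the patient"'s reference value. Protocol 10.1 ends the same definition with "reference eGFR)) at Day 28". The bullets in SAP 2.1.1, 4.1 and 8.1 agree with the protocol.

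**First working rule.** SAP 2.1.1 then states: "Percentage loss of eGFR determined algorithmically will be based on a comparison of eGFR at screening compared to an algorithmically determined reference creatinine value". SAP 4.1 repeats this for Day 28, and SAP 4.2 for Days 14 and 90. It sets screening against reference and uses no follow-up value.

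**Second working rule.** SAP 3.10.3 introduces a formula for the Day 28 loss, with screening eGFR as the comparator. SAP 3.10.4 and 3.10.5 repeat the pattern. The Day 14 version reads "Percentage loss in eGFR at Day 14 = 100% times [Screening eGFR - (Day 14 eGFR) / Screening eGFR" before the bracket closes. In 3.10.3 the consequence of a loss of 37% or more is "then patient fails key secondary endpoint", although Day 28 is the primary time point.

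**Related text.** SAP 3.10.2 computes screening eGFR from the pre-dose creatinine. The Day 90 eGFR formula in 3.10.5 takes Day 14 creatinine as its input. The SAP gives eGFR formulas for screening and for Days 14, 28 and 90, but none for the reference value. SAP section 1 gives the SAP precedence over the protocol.

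**The concern.** The eGFR criterion is one of three components of the primary endpoint, and the SAP gives three rules for it that cannot all be followed. A patient who entered on creatinine has a screening value at least twice reference, so screening eGFR is already the injured value. Loss measured from it shows whether the kidney got worse after enrolment. It does not show whether function came back.

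Each working rule fails in its own way:

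- With the bracket repaired, the screening formula passes patients who never recover.
- As printed, it fails nearly everyone.
- The screening-versus-reference sentence fixes the result before dosing.

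No planned sensitivity analysis would show the problem. SAP 3.10.7 varies how Day 28 creatinine is chosen, and 3.10.1 and 3.10.2 vary reference creatinine and AKI stage. None varies the comparator. If the rule is picked after unblinding, the primary endpoint has been chosen after seeing the data.

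**Working it through.** **Inputs.** MDRD exponent −1.154 (SAP 3.10.2 to 3.10.5). Loss limit 37% (protocol 12.1, SAP 2.1.1). Entry at 2.0-fold or more (Stage 2) or 3.0-fold or more (Stage 3) of reference creatinine, when entry is by creatinine (protocol 6.1). Success rates 75% and 50%, 60 per arm, one-sided α = 0.05, stated power 89% (SAP 2.1.2).

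**The plan's power figure.** The standard error under the null is √(2 × 0.625 × 0.375 / 60) = 0.0884. Under the alternative it is √((0.75 × 0.25 + 0.50 × 0.50) / 60) = 0.0854. Power = Φ[(0.25 − 1.645 × 0.0884) / 0.0854] = 0.890, as stated. The question is whether the 75% and 50% rates describe the variable that would be computed.

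**Limit on the creatinine scale.** Within a patient the age, sex and race terms cancel, so eGFR ratio = (creatinine ratio)^−1.154. A 37% loss leaves 0.63, and the creatinine ratio is 0.63^(−1/1.154) = 1.49.

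**Protocol rule.** A patient fails when Day 28 creatinine is at least 1.49 × reference. This nearly matches the cut of 1.5 × reference for complete recovery in the earlier post-hoc analysis (protocol 4.1.3.3.3). SAP 2.1.1 also describes success as complete recovery.

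**Screening baseline, bracket repaired.** The limit becomes 1.49 × screening creatinine:

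- Screened at 2 × reference: 1.492 × 2 = 2.98 × reference. Losses from reference up to 1 − 0.63 × 2^−1.154 = 71.7% still pass.
- Screened at 3 × reference: 1.492 × 3 = 4.48 × reference. Losses up to 1 − 0.63 × 3^−1.154 = 82.3% still pass.

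**Formula as printed.** 100% × [S − D/S], with S screening and D follow-up eGFR, passes only if D > S(S − 0.37). For S = 20 that is 20 × 19.63 = 393. At S = 20 and D = 60 the computed loss is 100% × (20 − 3) = 1700%.

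**Screening against reference.** The loss is 1 − 2^−1.154 = 55.1% at 2 × reference and 1 − 3^−1.154 = 71.9% at 3 ×. Every patient at 2 × or more fails before treatment can act.

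**Side by side.** Assumed patient: non-Black man aged 60, reference creatinine 1.0 mg/dL, reference eGFR 76.2. Only the as-printed column depends on these choices.

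| Screening → Day 28 creatinine | Loss from reference (protocol) | Screening baseline, bracket repaired | As printed | Screening v reference |
|---|---|---|---|---|
| 2.0 → 1.0 | 0%, pass | −122.5%, pass | 3202.7%, fail | 55.1%, fail |
| 2.0 → 2.0 | 55.1%, fail | 0%, pass | 3325.2%, fail | 55.1%, fail |
| 3.0 → 4.0 | 79.8%, fail | 28.3%, pass | 2073.5%, fail | 71.9%, fail |
| 1.0 → 2.0 (entry on urine output) | 55.1%, fail | 55.1%, fail | 7577.1%, fail | 0%, pass |

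**Effect on power.** The documents give no creatinine distribution, so trial-level success rates cannot be computed. Suppose the lenient screening baseline raises placebo success and narrows the difference. Under assumed rates (60 per arm, one-sided 0.05), power is 54% for 75% v 60%, 63% for 85% v 70%, 39% for 85% v 75%, and 35% for 80% v 70%.

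**The case against.** The best reply is that this is a drafting slip whose intent is plain. The SAP states the reference-based definition three times, SAP 3.10.1 builds a detailed reference-creatinine algorithm, and 3.10.6 has a rule for replacing that reference. The precedence clause settles conflicts between protocol and SAP. It does not settle conflicts inside the SAP, where the endpoint bullets agree with the protocol. The 3.10.3 formula is also tied by its own wording to a secondary endpoint. All of this is fair, and it makes a reference-based intent likely. But the screening comparator appears at all three time points, and it is the only loss formula a programmer could code. The natural repair of the bracket leaves it in place.

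Three limits on the size of the problem stand:

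- Patients who entered on urine output may have a screening creatinine near reference, and for them the two baselines nearly coincide. The criterion would then differ in strictness by entry route, which is a further fault.
- With the bracket repaired, some eGFR test remains. It still fails a patient whose creatinine rises to 1.49 times screening or more. To say that the endpoint becomes little more than alive and off dialysis is an approximation, and it applies to patients who entered on creatinine.
- The as-printed formula makes no dimensional sense and would probably be noticed. Its failures are also not universal: at S = 5 a pass needs D above 5 × 4.63 = 23, and at S = 8 above 8 × 7.63 = 61.

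**Conclusion.** The concern holds. The SAP's working rules for the eGFR criterion conflict with the protocol and with the SAP's own endpoint definition, and following any of them would misclassify patients on the primary endpoint. The failure limit moves from 1.49 × reference creatinine to 2.98 × or 4.48 × for patients screened at 2 × or 3 × reference. Under the other two readings, full recovery from 2 × reference counts as failure in the worked example.

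The creatinine limits rest only on the MDRD exponent and on the age, sex and race terms cancelling within a patient. The 2 × and 3 × cases apply to patients who entered on a creatinine rise. The effect on arm-level success rates is unknown, and the power figures for other rates are illustrations. The stated power is correct for the rates it assumes, but those rates have no stated basis under any of the working rules. This must be corrected before unblinding.

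**What to change.** In SAP 3.10:

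- Define Reference eGFR = 175 × (reference creatinine from Exhibit 1)^−1.154 × (age)^−0.203 × the sex and race terms already used in 3.10.2.
- Replace the loss formulas in 3.10.3 to 3.10.5 with 100% × (Reference eGFR − Day X eGFR) / Reference eGFR, for X = 14, 28 and 90.
- Use Day 90 creatinine in the Day 90 eGFR formula.
- Change the Day 28 label in 3.10.3 to the primary endpoint.
- Delete the screening-versus-reference sentence in 2.1.1, 4.1 and 4.2.

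One related point should be settled in the same edit. When there is no historical creatinine, SAP 3.10.1 back-calculates it from an eGFR of 75 with constant 186, while the eGFR formulas use 175. The assumed 75 then returns as about 75 × 175/186 = 70.6 (70.3 to 71.0 in worked cases, because the SAP's exponent −0.887 is not exactly −1/1.154). The SAP should say which value serves as reference eGFR for these patients.

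The cost is SAP wording and a few lines of derivation code. No new data are needed.
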